**\*investigators who may obtain informed consent**

**Extramural Associate Investigator**

[name] M.D., Endocrinology Unit, Queen's Medical Research Institute, Centre for Cardiovascular Science, University of Edinburgh, [name]

**Proposed Start Date:** June 1, 2011

**Estimated Duration of Accrual:** Five years

**Subjects of Study:** Men and women (35 - 70 yrs) with glucose intolerance

**Number:** 80

**Project uses ionizing radiation?** No

**Off-Site project?** No

**Multi-Institutional Project?** No

**Precis**

The hormone cortisol is a key regulator of metabolism that influences the use of glucose (sugar) and fat as fuels. Persistently increased cortisol levels, as in Cushing's syndrome, lead to obesity, type 2 diabetes mellitus and lipid abnormalities including elevated triglyceride levels and low high-density lipoprotein (HDL) levels. These same disorders are also present in patients without Cushing's syndrome, suggesting that cortisol may be involved in their pathogenesis. Mifepristone is a cortisol-like drug that blocks cortisol action in the body. It can reverse lipid abnormalities, diabetes and obesity in Cushing's syndrome patients but its effects on these conditions have not been tested in patients without the syndrome.

The long-term aim of this clinical trial is to evaluate the ability of mifepristone to reverse or improve glucose intolerance, dyslipidemia, hypertension and weight gain. An initial 7-day

prospective, randomized, placebo-controlled, crossover study is proposed here to look at the effect of short-term administration of oral mifepristone or placebo on glucose intolerance. Given that there are no human data available on the effect of mifepristone on insulin sensitivity, this will be a pilot study of 15 subjects. Data from this study will then be used to design a larger trial to evaluate long-term effects on blood pressure and weight, as well as glucose and triglyceride control.

Overweight or obese subjects with abnormal glucose tolerance will undergo each of the two treatments in a randomized order, including mifepristone by mouth and a look-alike inert tablet by mouth. Each treatment study will include two or three days of baseline tests that will be repeated after seven days of treatment. Treatments will be separated by at least six and no more than eight weeks. The tests will include blood drawing, urine collection, administration of glucose and insulin by vein, and a cortisol-like material to evaluate the metabolism of cortisol and a related hormone, corticosterone.

## BACKGROUND

Cortisol is an important regulator of metabolism that modulates the use of glucose and fat as fuels. Elevated cortisol levels in Cushing's syndrome lead to obesity, hypertension, dyslipidemia with elevated triglyceride (TG) levels and low high-density lipoprotein (HDL) levels, and type 2 diabetes mellitus (1). These disorders also are common in the general population, in the absence of Cushing's syndrome. In people without Cushing's syndrome, the constellation of abnormalities is often referred to as the "Metabolic Syndrome" based on the extent of the abnormalities. Some individuals with Metabolic Syndrome seem to have mild functional hypercortisolism, which may contribute to the pathogenesis of the syndrome (2 - 5). Also, some individuals with abdominal obesity have increased urinary free cortisol (UFC) levels, loss of diurnal cortisol rhythm, and abnormal HPA axis suppression after dexamethasone (5 - 6), similar to the biochemical abnormalities seen in Cushing's syndrome. Excess glucocorticoids in Cushing's syndrome are known to favor visceral fat deposition (7). However, many individuals with obesity do not have abnormal cortisol tests (8). Taken together, these data have led to the hypothesis that cortisol may be involved in development of abdominal obesity, glucose intolerance and other components of the Metabolic Syndrome, either because of subtle increases in circulating levels, or because of increased tissue exposure due to local metabolism.

### *Associations between tissue levels of cortisol, obesity and glucose tolerance*

Circulating cortisol levels are mostly normal in people with central obesity, insulin resistance Metabolic Syndrome (2 - 3), leading to speculation that increased local tissue exposure to cortisol or its active metabolites may be critical in development of these disorders. One possibility is that there is increased local regeneration of cortisol from corticosterone. The 11 $\beta$ -hydroxysteroid dehydrogenase (11BHS) enzymes interconvert hormonally inactive glucocorticoids such as cortisone and dehydrocorticosterone and their active forms, cortisol and corticosterone. The renal 11BHS2 enzyme catalyzes the conversion of cortisol to (inactive) cortisone, thus reducing mineralocorticoid effects of cortisol. The 11BHS1 enzyme is more widely expressed (in liver, adipose, bone, and the central nervous system) and functions primarily as a reductase (converting cortisone to cortisol) (9 - 10). This 11BHS1 reductase activity requires subcellular NADPH cofactor generation by hexose-6-phosphate dehydrogenase, and in its absence, this bi-directional enzyme can convert cortisol to cortisone. Intracellular cortisol levels may thus be modulated by conversion of cortisone to cortisol by 11BHS1, and this may contribute to the development of glucose intolerance and the Metabolic Syndrome (11).

Because urinary levels of cortisol, cortisone, and their metabolites reflect integrated (total) body metabolism (including the kidney), they cannot be used to assess the contribution of specific tissue components. As a result, 11BHS effects have been assessed using enzymatic assays of activity, measurement of mRNA expression in specific tissues, or measurement of conversion of cortisol or cortisone labeled with stable isotopes.

11BHS1 expression and activity has been found to be elevated in both visceral and subcutaneous fat depots in obese individuals (12 - 13). Purnell and colleagues studied eight obese men before and after weight loss and looked at daily cortisol production and clearance rates, intraabdominal fat (IAF) and subcutaneous fat (SQF) by computerized tomography, insulin

sensitivity ( $S_i$ ) by frequently sampled intravenous glucose tolerance tests, and subcutaneous adipocyte 11BHS1 gene expression by quantitative RT-PCR. They found that increased cortisol production rates and free cortisol levels correlated with increased IAF and decreased insulin sensitivity but not with subcutaneous fat. Increased 11BHS1 expression correlated with both IAF and SQF and with decreased  $S_i$ . With greater loss in body fat than lean mass with weight loss, 11BHS1 expression was found to be decreased from baseline (13). These data support a role for increased local (tissue) cortisol exposure leading to visceral fat deposition and insulin resistance.

Many investigators have suggested that increased cortisol release from the omentum into the portal vein contributes to hepatic insulin resistance associated with central obesity. However *in vivo* studies of obese non-diabetic individuals using stable isotopes suggest that splanchnic cortisol is derived entirely from the liver and that there is no cortisol release from the visceral tissue into the portal vein (–14 - 15). On the contrary, visceral tissue releases cortisone into the portal venous system, thus potentially providing increased substrate for hepatic conversion to cortisol (9). This cortisone release from the visceral tissue occurs in the presence of low levels of 11BHS2 mRNA in visceral fat. Therefore the exact mechanism by which cortisone is generated is not clear. It is possible that in some situations 11BHS1 has a predominately dehydrogenase (inactivating) activity leading to cortisone production (16 - 17).

It should be mentioned that some studies do not show a depot difference in 11BHS1 mRNA expression and have suggested that under steady state conditions, increased local production of cortisol is unlikely to contribute to omental adipose tissue function (18). These discrepancies in study results are likely related to differences in assays for measuring 11BHS activity, the use of different cells or explants and the effects of renal 11BHS2. Also, *in vitro* studies may not faithfully reproduce the *in vivo* environment, and therefore may result in a false preponderance of reductase or dehydrogenase activity.

Although glucocorticoids have been shown to induce 11BHS1 expression *in vitro*, a single study looking at omental levels of 11BHS1 in Cushing's syndrome patients found its expression to be similar to those of lean individuals (19). However, as omental fat mass is generally increased in patients with Cushing's syndrome, the net hormonal conversion cannot be ascertained. Moreover, it is possible that high cortisol levels overwhelm the 11BHS1 enzyme, as seen with 11BHS2 enzyme in the kidneys (20), so that excess cortisol is delivered to the liver.

Genetically engineered mouse models provide additional evidence for a potential pathologic role for 11BHS. Mice that over-express 11BHS1 in the liver develop fatty liver, hypertension, and mild insulin resistance without altered fat depot mass (21). On the other hand, transgenic mice overexpressing 11BHS1 selectively in adipose tissue exhibit a full metabolic syndrome with visceral obesity, hyperlipidemia, insulin resistance/diabetes and hypertension (22).

Other types of local cortisol metabolism may contribute to excess tissue glucocorticoid exposure. Reduction of glucocorticoids to A-ring reduced dihydro- and tetrahydro-derivatives by means of hepatic 5  $\alpha$ - and 5  $\beta$ -reductases was previously regarded as the final inactivation pathway. However, studies in rats have shown that corticosterone, 5  $\alpha$ - tetrahydrocorticosterone (5 $\alpha$ THB), and 5  $\alpha$  –dihydrocorticosterone (5 $\alpha$ DHB) are similarly effective in displacing tritiated dexamethasone from binding sites in hepatocytes while the 5 $\beta$  metabolites have less effective binding. In addition, 5 $\alpha$ THB, but not the 5 $\beta$ -reduced metabolites, activated the glucocorticoid receptor *in vitro* and suppressed ACTH *in vivo*, and these effects were inhibited by mifepristone (23). Increased 5 $\alpha$  reduced metabolites have also been seen in patients with diabetes and women with polycystic ovary syndrome (PCOS). These findings suggest that this pathway may be involved

in the development of glucose intolerance and Metabolic Syndrome (24 - 25).

The link of cortisol to insulin resistance and the Metabolic Syndrome is further substantiated by studies looking at the effects of mifepristone. Liu and colleagues investigated the role of tissue glucocorticoids in type 2 diabetes mellitus and obesity by analyzing the expression of glucocorticoid receptor and 11BHS1 in the hepatocytes of db/db mice (a model of type 2 diabetes mellitus). Increased expression of glucocorticoid receptor and 11BHS1 was associated with elevated levels of corticosterone, insulin, and blood glucose. They also found that intraperitoneal administration of mifepristone to the db/db mice for 3 weeks improved glucose tolerance with simultaneous decrease in the expression of 11BHS1 and glucocorticoid receptor in the liver (26). These findings were corroborated in another study on ob/ob diabetic mice (27). Also, administration of mifepristone to obese Zucker rats and db/db mice prevents high fat diet-induced weight gain and type-2 diabetes (28 - 29).

In humans, mifepristone successfully ameliorated hypercortisolemia-related effects in patients with Cushing's syndrome (30). More recently mifepristone was approved by the FDA for treatment of chronic hyperglycemia of uncontrolled Cushing's syndrome (31). In healthy men, administration of 400 mg of mifepristone at 2200h led to a decrease in triglyceride levels, despite compensatory increases in cortisol (32). Bertagna et al. looked at the antiglucocorticoid effect of mifepristone in four healthy men and found that ACTH and cortisol values increased 6 - 10 hours after administration of 400 mg of mifepristone at 0200 h, but not at 1400 h. Although this was a small study, it demonstrates the fact that the antiglucocorticoid effect of mifepristone on the hypothalamic-pituitary unit may occur only at certain times of the day (33), and supports the use of a split dosing regimen rather than a single daily dose, to minimize effects on ACTH.

Based on the putative role of excessive exposure to cortisol, we hypothesized that reduction in cortisol action with mifepristone might reverse glucose intolerance and some of the other components of the metabolic syndrome, just as it reverses the features of Cushing's syndrome (30).

The long-term aim of this study is to evaluate the ability of mifepristone to reverse or improve the components of Metabolic Syndrome, specifically impaired fasting glucose, dyslipidemia, hypertension and visceral obesity. This pilot study will specifically investigate the effects of short-term administration of mifepristone on insulin sensitivity. A second phase of the study will then look at the effects of long-term treatment on lipids, blood pressure, weight as well as glucose intolerance.

## **STUDY HYPOTHESIS**

The primary study hypothesis is that glucose abnormalities in overweight and obese individuals will improve with short-term administration of the glucocorticoid antagonist mifepristone.

A secondary study hypothesis is that activation of the HPA axis will be minimal when mifepristone is administered in four divided daily doses of 50 mg.

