**Secondary Outcomes**

1. Change in fasting plasma glucose and insulin levels.
2. Change in area under the curve (AUC) insulin, AUCglucose/AUCinsulin, and insulin sensitivity index based on OGTT.
3. Change in pre- and post-prandial glucose levels.
4. Change in basal triglyceride level.
5. Change in free fatty clearance based on the effect of insulin on FFA in the FSIVGTT.
6. Change in HDL, LDL, and total cholesterol levels.
4. Change in weight, BMI, neck, waist and hip circumference. It is unlikely that these parameters will change with the short duration of administration, however.
5. Change in blood pressure. It is unlikely that these parameters will change with the short duration of administration, however.
6. Whole-body rate of regenerating cortisol (measured with 9,11,12,12-[(2)H(4)]cortisol tracer) will be analyzed in collaboration with [name]. On metabolism by dehydrogenation, d4F loses 11alpha- deuterium, forming trideuterated cortisone (d3E) and is regenerated by reduction to tri-deuterated cortisol (d3F). 11BHSD1 reductase activity can be measured specifically as conversion of d3E to d3F (40). The amount of regenerated cortisol at baseline will be assessed for correlation with basal measures of insulin sensitivity and triglyceride levels, and the change in these parameters in response to mifepristone.
7. Adverse events will be tallied and compared between treatments.

8. Change in total and free testosterone, androstenedione, DHEAS, ACTH and cortisol will be assessed between treatments as a measure of mifepristone effect.
9. Change in 5 alpha and beta-reduced cortisol metabolites, cortisol, cortisone and their tetra-hydro metabolites will be assessed between treatments.
10. Correlation between post-treatment mifepristone level and the change in triglyceride levels and insulin sensitivity in response to mifepristone.

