## STUDY ANALYSIS

The study will be analyzed in collaboration with [name], Ph.D. (Biostatistics and Clinical Epidemiology Service, Clinical Center). Subjects will be randomized in blocks of 6 into the two treatment arms. Means and standard deviations will be used to describe continuous data. Proportions and frequencies will be used to describe categorical data. All continuous data will be examined for normality and homogeneity of variances, and will be either transformed as appropriate or assessed using non-parametric tests. The change in continuous variables (including triglyceride, HDL, LDL and total cholesterol levels, insulin sensitivity index, pre- and post-prandial glucose values, whole body cortisol production rates, blood pressure, weight, and waist circumference) before and after study intervention will be analyzed using paired t-tests or Wilcoxon signed-rank test. Correlation of continuous data (e.g., regenerated cortisol and insulin sensitivity and triglyceride levels, and mifepristone level and insulin sensitivity and triglyceride response) will be carried out by Pearson's correlation coefficient or Spearman's rho, as appropriate. Between and within treatment comparisons will be done using Mixed Models for a crossover design that will also consider sequence effect, if any. Difference in the proportion of subjects who meet criteria for metabolic syndrome, or other categorical data, before and after study intervention will be analyzed using McNemar's test. Two-sided p-values will be used for all analysis and the level of statistical significance will be set a priori at 0.05. The stepdown Bonferroni correction will be used to adjust for multiple comparisons. All statistical analysis will be performed using SAS v. 9.2 (SAS Institute, Cary, NC).

Human data on the effect of mifepristone on insulin sensitivity index are lacking. This will therefore be a pilot study of 17 subjects. Data from this study will then be used to design a long-term study looking at the effect of mifepristone on glucose intolerance, lipids, weight and blood pressure. With an estimated loss-to-follow-up rate of 15%, we would need to recruit a total of 25 patients. Thus, we plan to screen approximately 80 patients to account for the high ineligibility rate and patient drop-outs prior to study initiation.

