Based on current evidence, a compensatory rise in ACTH levels has been seen with mifepristone in healthy individuals at doses as low as 100 mg/day (when used as a single dose over 3 months) and 200 mg/day over 8 days (41 - 42). Given the uncertainty in the effect of the dose, we plan to do an interim analysis looking at the effect of the proposed dose (50 mg every 6 hours) on the HPA axis in the first 6 subjects (one randomization block). The data from the first 6 subjects will be unblinded to [name], the study statistician, only. If the 24 hour UFC value post mifepristone treatment is more than or equal to twice the upper limit of normal in four or more of the six subjects, then we will decrease the mifepristone dose to 25 mg every 6 hours (100 mg/day). However, if there is no significant increase in the levels (< twice the upper limit of normal), same dose of mifepristone will be continued throughout the study. If the mifepristone

dose is changed based on the results of the interim analysis, then the data from the first six subjects will not be used in the final analysis and 15 additional subjects will be enrolled prior to completion of the study. On the other hand, if no dose adjustment is required, the study analysis will be done as previously planned.

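### The secondary hypothesis says HPA activation will be minimal, but the final analysis designates no HPA measure for it and states only a p-value criterion, which cannot show that a rise is small

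*Combined protocol and SAP*

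**What the plan says.** The STUDY HYPOTHESIS section gives as its secondary hypothesis that "activation of the HPA axis will be minimal when mifepristone is administered in four divided daily doses of 50 mg". No measure, comparator or level accompanies it.

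Among the Secondary Outcomes, the item on androgens, ACTH and cortisol ends "ACTH and cortisol will be assessed between treatments as a measure of mifepristone effect". The urinary item reads "Change in 5 alpha and beta-reduced cortisol metabolites, cortisol, cortisone and their tetra-hydro metabolites will be assessed between treatments". Neither refers to the hypothesis. The Day 1 procedures take ACTH and cortisol hourly for 24 hours with a urine collection over the same time, and these are repeated on treatment. No mean, AUC or peak is chosen for analysis.

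STUDY ANALYSIS states "Between and within treatment comparisons will be done using Mixed Models for a crossover design" and "Two-sided p-values will be used for all analysis and the level of statistical significance will be set a priori at 0.05", and adds a step-down Bonferroni correction. It mentions no confidence interval, margin or equivalence test. It plans 17 subjects; the Precis says 15.

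The interim paragraph of STUDY ANALYSIS looks at the HPA axis in the first six subjects. The dose is lowered if 24-hour UFC after mifepristone is at or above "twice the upper limit of normal in four or more of the six subjects". Otherwise, "if there is no significant increase in the levels (< twice the upper limit of normal), same dose of mifepristone will be continued". If the dose is unchanged, the analysis proceeds as already planned. If it changes, those six subjects leave the final analysis. The same paragraph says that "a compensatory rise in ACTH levels has been seen with mifepristone in healthy individuals at doses as low as 100 mg/day", with the qualifier that this was a single dose given over three months, and that a rise was also seen at 200 mg/day over eight days.

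**The concern.** The hypothesis concerns how large a rise is. A two-sided test against zero asks whether there is a rise. In a small trial the two come apart in both directions: a rise that matters can be non-significant, and a trivial one can be significant. The multiplicity correction widens the gap, because it makes non-significance more likely and so makes an unproven small rise look better supported.

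The protocol reports an ACTH rise at 200 mg/day over eight days, and this trial's daily total is 4 × 50 = 200 mg. The size of any rise under split dosing is therefore the useful quantity, including for the longer trial that this pilot is meant to inform. At stake is whether the report can say anything reliable about HPA activation. The primary outcome, insulin sensitivity, is not touched.

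**Working it through.** The documents give no SD, margin or power for the HPA hypothesis, so there is no planned figure to reproduce. Continuous results below are in SDs of the within-subject mifepristone-minus-placebo difference.

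**Inputs.** n = 17 (STUDY ANALYSIS) and n = 15 (Precis); two-sided alpha 0.05; crossover model with n − 2 degrees of freedom and near-balanced sequences (assumed).

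**1. What a non-significant result leaves open.** The 95% CI half-width is t(0.975, n − 2)/√n. A just non-significant rise equals the half-width, so its CI runs from 0 to twice that value.

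- n = 17: 2.1314/√17 = 0.517 SD; upper limit 2 × 0.517 = 1.03 SD.
- n = 15: 2.1604/√15 = 0.558 SD; upper limit 2 × 0.558 = 1.12 SD.
- With an observed difference of exactly zero, the upper limit is the half-width: 0.52 SD (n = 17) or 0.56 SD (n = 15).
- A plain paired t-test (n − 1 df) gives nearly the same upper limits for the borderline case: 1.03 and 1.11 SD.

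**2. How often a real rise is missed.** Two-sided paired t-test, noncentral t, at an assumed true rise of 0.5 SD. The family for the step-down correction is not defined, so family sizes of 5, 10 and 20 are assumed. The adjusted columns are for the strictest step; later steps are less strict.

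| n | alpha 0.05 | 0.05/5 | 0.05/10 | 0.05/20 |
|---|---|---|---|---|
| 17 | 51% missed | 76% | 84% | 89% |
| 15 | 56% missed | 81% | 87% | 92% |

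At 0.05/10 and n = 17 the borderline observed rise becomes 0.80 SD. Its unadjusted 95% CI is 0.80 ± 0.52, about 0.28 to 1.32 SD. A rise whose interval excludes zero could thus be reported as non-significant.

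**3. What the interim rule can show.** The chance of at least 4 of 6 high values, if a share p of subjects truly reach twice the upper limit of normal, is binomial: 7% at p = 0.3, 34% at p = 0.5, 74% at p = 0.7. Three high values of six keep the dose, yet the exact 95% upper limit for the share is 88%.

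**4. The same UFC level used in the full sample.** Exact (Clopper-Pearson) 95% upper limits for the share of subjects with high UFC:

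| High values | n = 17 | n = 15 |
|---|---|---|
| 0 | 19.5% | 21.8% |
| 1 | 28.7% | 31.9% |
| 2 | 36.4% | 40.5% |
| 3 | 43.4% | 48.1% |

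**The case against.** The strongest reply is that the plan does address the question. The interim analysis examines the same dose and the same axis, with a named measure, level and count, and reaching that count would plainly weigh against the hypothesis. ACTH, cortisol and urinary cortisol are listed outcomes, and the mixed model yields estimates whether or not intervals are mentioned. This is a pilot and the hypothesis is secondary.

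Much of that stands, and it rules out some stronger readings:

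- A reader might infer that no planned result could bear on the hypothesis. The interim rule does bear on it. What remains is that the rule is a dose trigger in six subjects and is not carried into the final analysis.
- A reader might infer that the sponsor will report p > 0.05 as minimal activation. The documents do not say so. They state no other criterion and nothing that prevents it.
- A reader might take a rise at this regimen as already established. The 100 mg/day finding was a single dose over three months. The protocol speaks of uncertainty about the dose effect, and the Background cites a small study with no ACTH or cortisol rise after an afternoon dose. Whether split dosing produces a rise is partly open, so a between-treatment comparison is relevant.
- A reader might take UFC below twice the upper limit of normal as the definition of minimal. The documents never make that link.

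The 1.03 SD limit is a borderline case, which is why the zero-difference limit is shown beside it. Finally, a count of high UFC values on mifepristone alone would be a poor measure of activation: the Background says some people with abdominal obesity already have raised UFC, and UFC is not an exclusion criterion.

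**Conclusion.** The point holds, at minor severity. For the final analysis, no HPA measure or profile summary is designated for the secondary hypothesis, and the only stated criterion cannot show that a rise is small. At n = 17, non-significance is compatible with rises up to 1.03 SD in the borderline case, and with rises up to 0.52 SD even when the observed difference is zero.

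These figures assume near-balanced sequences, roughly normal paired differences and complete data. They cannot be put into cortisol or ACTH units because the documents give no SD. The adjusted miss rates also depend on the assumed family size. The conclusion that the criterion does not match the claim depends on none of these.

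**What to change.** State in STUDY ANALYSIS that the secondary hypothesis will be evaluated by estimation, as follows.

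- Report the mifepristone-versus-placebo difference or ratio in 24-hour mean cortisol, 24-hour mean ACTH and 24-hour UFC, with unadjusted 95% CIs. Use the crossover mixed model already planned, on the log scale if the data are skewed, with each period's baseline accounted for.
- Report descriptively the proportion of subjects with UFC at or above twice the upper limit of normal on mifepristone, with an exact 95% CI, beside the same proportion on placebo and at baseline.
- State that p > 0.05 will not be taken as support for minimal activation.
- If the dose changes at the interim, report the 50 mg subjects separately, since they leave the final analysis and the hypothesis names that dose.

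No change to the dose rule is proposed.

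The cost is plan wording and reporting; the hourly samples and 24-hour urine are already scheduled. The downside is that the trial may be unable to claim minimal activation: even 0 of 17 high UFC values leaves an upper limit of 19.5%.
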